5.6 Definition of the start and the end of the trial

The start of the trial is defined as the date of screening of the first volunteer. The end of the trial is defined as 12 months after the date of the last visit of the last volunteer to allow for sample processing and data analysis.

5.7 Potential benefits for the volunteers.

Volunteers will not benefit directly from participation in this study. However, it is hoped that the information gained from this study will contribute to knowledge about nasal colonisation

and therefore to the development of a safe and effective nasal vaccine in the future. Volunteers will also receive information about their general health status.

5.8 Involvement of the NHS Research Ethics Committee

This study protocol has been submitted to Hampshire A Regional Ethics Committee (REC) for approval of this human challenge study.

6. Inoculum

6.1 Selection of strain of *N. lactamica*

A wild-type strain of *Neisseria lactamica* strain Y92-1009 (sequence type 3493, clonal complex 613) will be used because we have previously used it safely in experimental challenge of over 250 human volunteers (Deasy, Guccione et al. 2015, Evans, Pratt et al. 2011).

6.2. Production of the inoculum

Stocks of *N. lactamica* Y92-1009 (sequence type 3493, clonal complex [CC] 613) in Frantz medium containing 30% (v/v) glycerol will be supplied by the Current Good Manufacturing Practices pharmaceutical manufacturing facilities at Public Health England (Porton Down, United Kingdom). Vials of 1×10^6 bacteria, suspended in Frantz medium containing 30% (v/v) glycerol, will be stored at -80°C and will be thawed and diluted in phosphate buffered saline (PBS) prior to inoculation, following the study specific SOP: **Preparation and monitoring of *N. lactamica* inoculum for human challenge studies.**

6.3 Quality assessment of the inoculum

Frozen stocks will be assessed for viability and contamination using standard microbiological procedures. Using these data a single batch will be prepared for storage at -80°C and subsequent human challenge. Stocks will be checked monthly for changes in viable counts.

6.4 Transport of the inoculum

The inoculum will be transferred to the University Hospital Southampton under temperature-monitored conditions. The aliquot will be placed into a container as secondary packaging. They will be placed inside leak and shock resistant transport boxes with secured lids.

6.5 Storage of the inoculum

The cell banks will be stored at -80°C in a locked, dedicated, temperature monitored freezer.

6.6 The optimal and safe dose of the inoculum

Based on the previous *N. lactamica* work it is estimated that 50% of volunteers will be colonised 1-2 weeks after inoculation with 10^5 cfu without any safety concerns (Deasy, Guccione et al. 2015). The hypothesis is that those who are colonised at day 4 will exhibit seroconversion by day 14, confirming biologically 'significant' colonisation.

6.7 Monitoring of the *N. lactamica* dose administered to volunteers

After the inoculum is given a sample of the residual inoculum will be diluted and cultured overnight. The dose will then be evaluated by viable count and the species confirmed by Polymerase Chain Reaction (PCR).

7. Recruitment and withdrawal of trial volunteers

7.1 Recruitment

Healthy volunteers will be recruited through various media. Care will be taken not to recruit from vulnerable groups (mental health or other capacity issues or those under 18 years old). The recruitment strategy will be approved by the Health Research Authority (HRA).

Volunteers may be recruited by use of an advertisement +/- registration form formally approved by the ethics committee and distributed or posted in the following places:

- In public places, including buses and trains, with the agreement of the owner / proprietor
- In newspapers or other literature for circulation
- On radio via announcements
- On a website operated by our group or with the agreement of the owner or operator (including on-line recruitment through our web-site)
- As a post on a Twitter, Facebook or Gumtree account owned and operated by our group
- Video message posted on the National Health Service (NHS) YouTube channel.
- By e-mail distribution to a group or list only with the express agreement of the network administrator or with equivalent authorisation
- By email distribution to individuals who have already expressed an interest in taking part in any clinical trial at the NIHR-WTCRF Southampton
- On stalls or stands at exhibitions or fairs
- Via presentations (e.g. presentations at lectures or invited seminars)
- Direct mail-out: This will involve obtaining names and addresses of adults via the most recent Electoral Roll. The contact details of individuals who have indicated that they do not wish to receive postal mail-shots would be removed prior to the investigators being given this information. The company providing this service is registered under the Data Protection Act 1998. Investigators would not be given dates of birth or ages of individuals but the list supplied would only contain names of those aged between 18-45 years (as per the inclusion criteria)
- Southampton NIHR-WTCRF Database of Healthy Volunteers: We may contact individuals from this database who have previously expressed an interest in receiving information about future studies for which they may be eligible

7.2 Volunteer information sheet

A volunteer information sheet will be given to the volunteer at least 24 hours before the screening visit. The volunteer information sheet will include all risks of participating in this study and safety measures that are involved in the study and will be formally approved as part of the HRA application.

7.3 Screening visit

Individuals who have expressed an interest in taking part in the study will be invited to attend a screening session after a short telephone screening. During the screening visit the study will be explained. If the volunteer has any questions they can be addressed during this visit. The screening visit can be up to 90 days prior to challenge on day 0.

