7.3.3 Screening investigations

A throat swab will be taken to look for *N. lactamica* and *N. meningitidis* carriage at screening. Females will have a pregnancy test. A nasal wash will be taken according to the SOP:

Collection of a nasal wash sample for culture and as a baseline for assessing mucosal immunogenicity. An ECG will be performed at screening or prior to inoculation.

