7.4.1 Exclusion criteria

The volunteer may not enter the study if any of the following criteria apply:

- Current active smokers
- *N. lactamica* or *N. meningitidis* detected on throat swab or nasal wash taken before the challenge
- Individuals who have a current infection at the time of inoculation
- Individuals who have been involved in other clinical trials involving receipt of an investigational product over the last 12 weeks or if there is planned use of an investigational product during the study period
- Individuals who have previously been involved in clinical trials investigating meningococcal vaccines or experimental challenge with *N. lactamica*
- Use of systemic antibiotics within the period 30 days prior to the challenge
- Any confirmed or suspected immunosuppressive or immune-deficient state, including HIV infection; asplenia; recurrent, severe infections and chronic (more than 14 days) immunosuppressant medication within the past 6 months (topical steroids are allowed)
- Use of immunoglobulins or blood products within 3 months prior to enrolment.
- History of allergic disease or reactions likely to be exacerbated by any component of the inoculum
- Contraindications to the use of ciprofloxacin, specifically a history of epilepsy, prolonged QT interval, hypersensitivity to quinolones or a history of tendon disorders related to quinolone use
- Any clinically significant abnormal finding on clinical examination
- Any other significant disease, disorder, or finding which may significantly increase the risk to the volunteer because of participation in the study, affect the ability of the volunteer to participate in the study or impair interpretation of the study data, for example recent surgery to the nasopharynx
- Occupational, household or intimate contact with immunosuppressed persons
- Pregnancy or lactation

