8.4.2 Review prior to the challenge

Prior to any procedure taking place the volunteer will be asked if he has any questions about the study and agrees to continue with the study. Eligibility will be reconfirmed before the challenge is conducted.

Medical history

The study doctor will take an interim medical history asking if there are any new medical issues since the screening visit. Special attention will be given to any possible signs of infection such as fever. If there are any significant abnormalities found, the challenge will be postponed at the discretion of the study doctor.

Physical examination

A physical examination will be conducted to check for any abnormalities. Vital signs including heart rate, blood pressure, respiratory rate and temperature will be recorded prior to the challenge procedure. If there are any significant abnormalities found, the challenge may be postponed at the discretion of the study doctor.

Laboratory investigations

A nasosorption test will be performed according to the SOP: **Collection of a nasosorption sample** to collect nasal fluid for assessment of mucosal immune responses. Two posterior pharyngeal swabs will then be taken according to SOP: **Collection of throat and nasal swabs (excluding samples for PCD) SCBR/GEN/270**. Saliva samples will be collected according to SOP: **Collection of saliva using an Oracol saliva swab**. Blood samples will be taken as a baseline for the assessment of cellular and humoral immunogenicity. Collection of all clinical samples will adhere to the UHS Standard Infection Control Precautions Policy (Version 5.0, 25/4/16). Assessment of shedding of *N. lactamica* will be carried out according to the study specific SOP: **Assessment of the environmental shedding of *N. lactamica***. This will involve analysis of a face mask worn for approximately an hour prior to study visits and / or speaking inside a cough box with air sampler.

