13.1 Endpoints of the study

Primary endpoint

- Rise in serological specific antibody titre comparing day 0 versus day 14 and 28 days post eradication and comparing early (day 4) versus late (day 14) eradication

Secondary endpoints:

- Assessment of colonisation – culture of *N. lactamica* from throat swabs at day 4 for group 1 and days 4, 7 and 14 for group 2
- Assessment of eradication – culture of *N. lactamica* from throat swabs on the day of eradication, one day, 10 days and 28 days after eradication
- Rise in mucosal specific antibody titre comparing day of screening versus day 14 and 28 days post eradication and comparing early (day 4) versus late (day 14) eradication
- Change in nasal cytokine profile comparing day 0 versus day 4, 14 and 28 days post eradication and comparing early (day 4) versus late (day 14) eradication
- Difference in environmental shedding between short (group 1) and longer (group 2) periods of colonisation.

Safety endpoints:

- Occurrence of unsolicited adverse events within the study period
- Occurrence of serious adverse events within the study period

Safety analysis will be carried out for all volunteers that received the inoculum, regardless of whether or not they complete the study.

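### The nasal-wash antibody baseline and the only carriage result known before inoculation may be up to 90 days old on day 0

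*Combined protocol and SAP*

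**What the plan says.** **Timing of screening.** Section 7.3: "The screening visit can be up to 90 days prior to challenge on day 0". Tables 10.1 and 10.2 repeat the 90-day limit.

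**What is sampled at screening.** Section 7.3.3 begins: "A throat swab will be taken to look for" carriage of *N. lactamica* and *N. meningitidis*. It also calls for a nasal wash, with this purpose: "Collection of a nasal wash sample for culture and as a baseline for assessing mucosal immunogenicity". In both tables the nasal wash appears at screening, on day 14 and 28 days after eradication (day 32 in Group 1, day 42 in Group 2). None is scheduled on day 0.

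**Eligibility.** Section 7.4.1 (exclusion criteria) rules out volunteers with either organism "detected on throat swab or nasal wash taken before the challenge", without limiting the age of the sample. Two further exclusions are tied to the challenge and not to the screening sample: "Use of systemic antibiotics within the period 30 days prior to the challenge" and "Individuals who have a current infection at the time of inoculation".

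**Endpoint.** Section 13.1 lists as a secondary endpoint: "Rise in mucosal specific antibody titre comparing day of screening versus day 14 and 28 days post eradication". The serum endpoint (primary) and the nasal cytokine endpoint (secondary) are both measured from day 0. The primary objective (4.1) covers systemic and mucosal humoral responses.

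**Day 0.** Section 8.4.2, in the review before inoculation: "Two posterior pharyngeal swabs will then be taken according to SOP". Section 11.2 sends one throat swab per time point for culture.

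**The concern.** The screening visit does two jobs that both depend on its being close to day 0.

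First, it supplies the baseline for nasal-wash antibody. A change measured from that sample includes whatever happened between screening and inoculation as well as the response to the challenge. Section 3.3 describes *N. lactamica* as spread by close contact and common in young children, and section 3.4 reports specific salivary IgA by 4 weeks after colonisation. An exposure early in a 90-day gap therefore has time to raise mucosal antibody before day 0. The groups are chosen by preference and not randomised (5.3), so nothing in the design balances the length of that gap between them.

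Second, it supplies the carriage result on which eligibility is decided. The carriage exclusion supports attributing day 4 carriage, and the antibody response of those colonised, to the inoculum. A negative result that is weeks old, or was obtained while the volunteer was taking an antibiotic, supports this less well.

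**Working it through.** The plan gives no figure of its own on this point, so there is nothing to reproduce. The check is date arithmetic on the stated windows.

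**1. Interval covered by the nasal-wash change.** Inputs: up to 90 days from screening to challenge (7.3); later washes on day 14 and on day 32 or 42 (Tables 10.1, 10.2); serum baseline on day 0 (13.1 and the tables). Longest nominal interval = 90 + day of the later sample.

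| Later sample | Nasal wash, longest | Serum |
|---|---|---|
| Day 14, both groups | 90 + 14 = 104 days | 14 days |
| Day 32, Group 1 | 90 + 32 = 122 days | 32 days |
| Day 42, Group 2 | 90 + 42 = 132 days | 42 days |

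At day 14 the ratio is 104 / 14 = 7.4. The visit windows of 2 days either way move wash and serum together, so the excess stays at up to 90 days. These are lengths of time, not estimates of bias.

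**2. Antibiotics and the screening swab.** Inputs: swab allowed from day -90; antibiotic use excluded only in the 30 days before challenge (7.4.1). Days on which a volunteer may be swabbed while on antibiotics and remain eligible: day -90 to day -31, which is 90 - 30 = 60 days. If the swab falls within the last 30 days, use on the swab day does exclude, but a course that ended shortly before the swab may still lie outside the window.

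**3. Can the day 0 swab serve as the eligibility check?** Section 11.2 allows up to 48 hours of incubation and then up to 24 hours of subculture: 48 + 24 = 72 hours at most. Inoculation is at the same visit (8.4), so this result comes too late to decide eligibility. It can identify an existing carrier afterwards.

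**4. What the plan does with a positive day 0 culture.** Three sections bear on it:

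- 7.4.1: the swab was taken before the challenge, so the volunteer is ineligible.
- 9.4: ineligibility found retrospectively is a ground for withdrawal, replacement is allowed, and withdrawn volunteers' data stay in the primary-objective analysis.
- 11.4: colonisation is at least one isolate cultured from day 4 onwards, with no reference to a negative day 0 culture.

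Read together, an existing carrier who is still positive on day 4 can be ineligible, analysed and counted as colonised. Recruitment to a group stops at 11 colonised (5.2), so one such volunteer is 1/11 = 9% of the group's target.

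**5. Baselines of the other samples.** Blood, saliva and nasosorption are all collected on day 0 in both tables. Saliva is not collected at screening, so the screening baseline named in 13.1 cannot apply to saliva IgA; for nasal wash it is the only one available.

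**The case against.** The best defence is that the plan has safeguards beyond the screening visit. Throat swabs are taken on day 0 before inoculation, so a carrier on that day can be found, and 9.4 allows withdrawal and replacement. The inoculum is a defined strain, sequence type 3493 (6.1), and isolates are stored for PCR and sequencing (11.2), so a different natural strain can be told apart from the inoculum. The primary serum endpoint has a same-day baseline.

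The antibiotic case is also remote. It needs a carrier who is on antibiotics when sampled, is suppressed below detection in both throat swab and nasal wash, is not cleared, and carries again by day 0. If the drug cleared carriage, the negative result was true. The detailed history at screening (7.3.2) and the general exclusion for findings that impair interpretation give the investigator some room to act.

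Most of this stands, and it rules out a stronger reading that might tempt a reader: that anyone who acquires *Neisseria* after screening simply passes unnoticed. The safeguards do not, however, replace the missing day 0 nasal wash. They work only after inoculation, and the colonisation definition in 11.4 uses neither the day 0 culture nor the sequencing result.

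**Conclusion.** The point holds as a cheap improvement to the design. The nasal-wash baseline may precede inoculation by up to 90 days, giving an interval to day 14 of up to 104 days against 14 for serum. The endpoint affected is secondary, but it serves the mucosal half of the primary objective. The carriage exclusion need not hold on day 0, and the plan has no consistent rule for a positive day 0 culture. The antibiotic gap of 60 calendar days is permitted by the text but is the lesser part.

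The documents do not support going further in three respects:

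- **Numbers affected.** They give no rate of natural acquisition, no distribution of screening intervals and no frequency of antibiotic use. A count out of 44 would need an invented rate, and an upper figure would need every volunteer screened on day -90.
- **Bias between groups.** Exposure before day 0 would inflate the within-group rise. It would bias the comparison of early with late eradication only if exposure or screening intervals differed by group. The design does not prevent that, but nothing in the documents indicates it.
- **Antibiotics and antibody.** The antibiotic point concerns culture for carriage. Nothing in the documents suggests that it distorts the nasal-wash antibody baseline.

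**What to change.** 1. **Sampling window.** In 7.3 and Tables 10.1 and 10.2, require the existing eligibility throat swab and nasal wash to be taken within a short stated window before challenge, with results available before inoculation. The rest of screening can keep 90 days. A limit of 30 days, for example, would cut the longest nasal-wash interval to day 14 from 104 to 30 + 14 = 44 days. That figure is a choice and not derived from the documents, and some gap remains.
2. **Antibiotic criterion.** Reconcile the exclusion in 7.4.1 with the date of the swab, so that it covers a period up to the swab as well as the time from swab to challenge.
3. **Day 0 culture.** State that a volunteer who is culture-positive on day 0 is not counted as colonised by the inoculum, nor towards the 11 per group. Reconcile 7.4.1, 9.4 and 11.4 on the eligibility and analysis of such a volunteer.
4. **Endpoint wording.** In 13.1, name the baseline for each mucosal sample: the pre-challenge wash for nasal-wash antibody, and day 0 for saliva.

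The cost is amendment wording and tighter scheduling, with no new type of sample. The downside is that a volunteer whose challenge slips beyond the window needs the swab and wash repeated.

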7.3.1 Informed consent

All volunteers will sign and date the informed consent form before any study specific procedures are performed. At the screening visit, the volunteer will be fully informed of all aspects of the trial, the potential risks and their obligations. The following will be emphasised:

- Participation in the study is entirely voluntary
- Refusal to participate involves no penalty or loss of medical benefits
- The volunteer may withdraw from the study at any time
- The volunteer is free to ask questions at any time to allow him or her to understand the purpose of the study and the procedures involved
- There is no direct benefit from participating
- The volunteer will be registered on the TOPS database (The Over-volunteering Prevention System; www.tops.org.uk)
- The aims of the study and all tests to be carried out will be explained. The volunteer will be given the opportunity to ask about details of the trial, and will then have time to consider whether or not to participate

The volunteer will be asked to sign and date two copies of the consent form, which will also be signed and dated by the investigator. One original will be given to the volunteer and the other will be stored in the NIHR-WTCRF. A copy will be stored in the volunteer's medical file.

7.3.2 Medical history and physical examination

A detailed medical history and physical examination will be conducted, making sure that all inclusion criteria and no exclusion criteria are met.

7.3.3 Screening investigations

A throat swab will be taken to look for *N. lactamica* and *N. meningitidis* carriage at screening. Females will have a pregnancy test. A nasal wash will be taken according to the SOP:

Collection of a nasal wash sample for culture and as a baseline for assessing mucosal immunogenicity. An ECG will be performed at screening or prior to inoculation.

7.4 Inclusion and exclusion criteria

7.4.1 Inclusion criteria

The volunteer must satisfy all the following inclusion criteria to be eligible for the study:

- Healthy adults aged 18 to 45 years inclusive on the day of enrolment
- Fully conversant in the English language
- Able and willing (in the investigator's opinion) to comply with all study requirements
- Written informed consent to participate in the trial
- Willingness to take an antibiotic regimen after inoculation according to the study protocol
- For females only, willingness to practice continuous effective contraception (see below) during the study and a negative pregnancy test on the day(s) of screening and inoculation

7.4.1 Exclusion criteria

The volunteer may not enter the study if any of the following criteria apply:

- Current active smokers
- *N. lactamica* or *N. meningitidis* detected on throat swab or nasal wash taken before the challenge
- Individuals who have a current infection at the time of inoculation
- Individuals who have been involved in other clinical trials involving receipt of an investigational product over the last 12 weeks or if there is planned use of an investigational product during the study period
- Individuals who have previously been involved in clinical trials investigating meningococcal vaccines or experimental challenge with *N. lactamica*
- Use of systemic antibiotics within the period 30 days prior to the challenge
- Any confirmed or suspected immunosuppressive or immune-deficient state, including HIV infection; asplenia; recurrent, severe infections and chronic (more than 14 days) immunosuppressant medication within the past 6 months (topical steroids are allowed)
- Use of immunoglobulins or blood products within 3 months prior to enrolment.
- History of allergic disease or reactions likely to be exacerbated by any component of the inoculum
- Contraindications to the use of ciprofloxacin, specifically a history of epilepsy, prolonged QT interval, hypersensitivity to quinolones or a history of tendon disorders related to quinolone use
- Any clinically significant abnormal finding on clinical examination
- Any other significant disease, disorder, or finding which may significantly increase the risk to the volunteer because of participation in the study, affect the ability of the volunteer to participate in the study or impair interpretation of the study data, for example recent surgery to the nasopharynx
- Occupational, household or intimate contact with immunosuppressed persons
- Pregnancy or lactation

